Table 14.2.3.1.1.1	Hb: Change from Baseline in Average of Week 20 and Week 24 (LOCF, FAS)																																																								
Table 14.2.3.1.2.1	Hb: Change from Baseline in Average of Week 20 and Week 24 by MMRM (FAS)																																																								
Table 14.2.3.2.1	Hb: Proportion of Subjects with $\geq 1.0$ g/dL Increase from Baseline (FAS)																																																								
Table 14.2.3.3.1.1	Rescue Therapy: Proportion of Subjects Received ESA (FAS)																																																								
Table 14.2.3.3.2.1	Rescue Therapy: Proportion of Subjects Received Red Blood Cell Transfusion (FAS)																																																								
Table 14.2.3.3.3.1	Rescue Therapy: Proportion of Subjects Received Phlebotomy (FAS)																																																								
Table 14.2.3.4.1.1	Average Dose of Study Drug (FAS)																																																								
Table 14.2.3.4.2.1	Distribution of Dose of Study Drug (FAS)																																																								

Table 14.2.3.5.1 Summary of Dose Adjustments of MT-6548 (FAS)
Table 14.2.3.6.1 Average Dose of Iron: Absolute and Change from Screening Period (FAS)
Table 14.2.3.7.1 Iron Supplementation: Proportion of Subjects Administered Iron Supplementation (FAS)
Table 14.2.3.8.1 Proportion of Subjects with Serum Ferritin <math>\geq</math>100 ng/mL or TSAT <math>\geq</math>20% (FAS)
Table 14.2.3.9.1.1 Serum Iron: Absolute, Change and Percent Change from Baseline (FAS)
Table 14.2.3.9.1.2 TIBC: Absolute, Change and Percent Change from Baseline (FAS)
Table 14.2.3.9.1.3 TSAT: Absolute, Change and Percent Change from Baseline (FAS)
Table 14.2.3.9.1.4 Serum Ferritin: Absolute, Change and Percent Change from Baseline (FAS)
Table 14.2.3.9.1.5 Hepcidin: Absolute, Change and Percent Change from Baseline (FAS)
Table 14.2.3.9.2.1 Serum Iron: Change and Percent Change from Baseline by MMRM (FAS)
Table 14.2.3.9.2.2 TIBC: Change and Percent Change from Baseline by MMRM (FAS)
Table 14.2.3.9.2.3 TSAT: Change and Percent Change from Baseline by MMRM (FAS)
Table 14.2.3.9.2.4 Serum Ferritin: Change and Percent Change from Baseline by MMRM (FAS)
Table 14.2.3.9.2.5 Hepcidin: Change and Percent Change from Baseline by MMRM (FAS)
Table 14.2.3.9.2.6 Serum Ferritin: Absolute by MMRM (FAS)

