#### 3.1.2 Other endpoints

- (1) Changes in mean Hb values from the first day of the treatment period at Week 20 and Week 24 of the treatment period
- (2) Proportion of subjects with a  $\geq 1.0$  g/dL increase from baseline in mean Hb values at each time point in the treatment period
- (3) Proportion of subjects receiving rescue therapy with ESA formulations, red blood cell transfusion, or phlebotomy
- (4) Study drug dosage
- (5) Total number of study drug dosage adjustments
- (6) Iron supplement dosage
- (7) Proportion of subjects receiving iron supplements via oral, intravenous, or any route.

- (8) Proportion of subjects with serum ferritin  $\geq 100$  ng/mL or TSAT  $\geq 20\%$
- (9) Changes and rate of changes in iron-related indices (serum iron, TIBC, TSAT, and serum ferritin levels) and hepcidin from the first day of the treatment period
- (10) Changes in hematocrit, red blood cell count, reticulocytes (count and rate), mean corpuscular volume, mean corpuscular hemoglobin, and erythropoietin from the first day of the treatment period
- (11) Changes and rate of changes in systolic blood pressure, diastolic blood pressure, lipids (total cholesterol, LDL-C, HDL-C, LDL-C/HDL-C ratio, triglycerides), and blood glucose from the first day of the treatment period
- (12) QOL indices (EQ-5D-5L, KDQOL)

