#### 7.1.2 Descriptive statistics to calculate

Types of descriptive statistics to be calculated for each variable are provided below.

Number of subjects, mean, standard deviation (SD), median, minimum, maximum, and 2-sided 95% CI of the mean

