(9) Changes and rate of changes in iron-related indices (serum iron, TIBC, TSAT, and serum ferritin levels) and hepcidin from the first day of the treatment period

Descriptive statistics should be prepared for measured values of iron-related measures (serum iron, TIBC, TSAT, and serum ferritin) and hepcidin at each evaluation time point of the treatment period and their change and change rates from the first day of the treatment period. A paired t-test should be performed for before and after comparison of changes and change rates from the first day of the treatment period.

LSMean, its standard errors, and 2-sided 95% CI should be calculated for the change in iron-related measures (serum iron, TIBC, TSAT, and serum ferritin) and hepcidin from the first day of the treatment period to each evaluation time point using the MMRM model (with compound symmetry [CS] for a variance-covariance matrix within subjects). Only the serum ferritin value at each evaluation time point of the treatment period should be analyzed similarly.

The time course diagram of changes in the iron-related measures (serum iron, TIBC, TSAT, and serum ferritin levels) and hepcidin from the first day of the treatment period to each evaluation time point should be prepared. The 95% CI of LSMean will be represented by an error bar. For only the serum ferritin value, a time course diagram should also be prepared for mean ferritin value at each evaluation time point of the treatment period. 95% CI of the mean will be represented by an error bar.

The serum ferritin values are shown as follows.

- The following scatter plot chart should be provided by treatment group. Linear regression should be performed to calculate the p-value and correlation coefficient of the test with zero slope as the null hypothesis.

x: Serum ferritin values at baseline

y: Serum ferritin values at Week 24 of the treatment period

- (10) Changes in hematocrit, red blood cell count, reticulocyte (count and rate), mean corpuscular volume, mean corpuscular hemoglobin, and EPO from the first day of the treatment period

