Descriptive statistics of hematocrit, red blood cell count, reticulocyte (number and rate), mean corpuscular volume, mean corpuscular hemoglobin, and EPO should be calculated at each evaluation time point. And, the change from the first day of the treatment period should be obtained, and the descriptive statistics should be calculated. A paired t-test should be performed for before and after comparison of changes from the first day of the treatment period.

LSMean, its standard errors, and 2-sided 95% CI should be calculated for the change in hematocrit, red blood cell count, reticulocyte (number and rate), mean corpuscular volume, mean corpuscular hemoglobin, and EPO from the first day of the treatment period to each evaluation time point using the MMRM model (with compound symmetry [CS] for a variance-covariance matrix within subjects).

A histogram of EPO measurements should be prepared for evaluation time point at Week 24 of the treatment period.

- (11) Changes in systolic blood pressure, diastolic blood pressure, and blood glucose from the first day of the treatment period, changes and the rate of change in lipid (total cholesterol, LDL-C, HDL-C, LDL-C/HDL-C ratio, triglycerides) from the first day of the treatment period

Systolic blood pressure, diastolic blood pressure, lipids (total cholesterol, LDL-C, HDL-C, LDL-C/HDL-C ratio, triglycerides), and blood glucose should be analyzed in the same manner as hematocrit, red blood cell count, and reticulocyte (count and rate) in the preceding section.

The change from the first day of the treatment period should be obtained, and the descriptive statistics should be calculated. A paired t-test should be performed for before and after comparison of changes from the first day of the treatment period. LSMean, standard error, and 2-sided 95% CI should be calculated for the change from the first day of the treatment period using the MMRM model (with compound symmetry [CS] for a variance-covariance matrix within subjects).

The descriptive statistics should be similarly calculated for the change rate from the first day of the treatment period at each evaluation time point of the lipid (total cholesterol, LDL-C, HDL-C, LDL-C/HDL-C ratio, triglycerides), and LSMean, standard error, and 2-sided 95% CI should be calculated using the MMRM model (with compound symmetry [CS] for a variance-covariance matrix within subjects).

- (12) QOL indices (EQ-5D-5L, KDQOL)

1) EQ-5D-5L

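### The paired t-test and MMRM on arithmetic percent change in iron indices and hepcidin are biased upward, so zero is the wrong null and a true fall is understated

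*SAP*

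**What the plan says.** SAP 3.1.2 (9) names the endpoint as "Changes and rate of changes in iron-related indices" and hepcidin. SAP 7.5.2 (9) then plans descriptive statistics for the measured values and "their change and change rates from the first day of the treatment period", followed by the test: "A paired t-test should be performed for before and after comparison of changes and change rates" from baseline. The MMRM sentence in that section speaks only of change. The corrected list of output tables in the errata (section 11) shows that change rate means percent change and extends the MMRM to it, for example "Hepcidin: Change and Percent Change from Baseline by MMRM (FAS". That list has a percent-change MMRM table for each of the five markers, and descriptive tables such as "Serum Ferritin: Absolute, Change and Percent Change from Baseline (FAS".

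The standard set of descriptive statistics in SAP 7.1.2 is "Number of subjects, mean, standard deviation (SD), median, minimum, maximum, and 2-sided 95% CI of the mean". It includes the median but no geometric mean. Neither document plans a log transform, a ratio or a rank test for these markers.

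For lipids, SAP 7.5.2 (11) says "The descriptive statistics should be similarly calculated for the change rate from the first day of the treatment period" and adds an MMRM on the change rate. Its t-test sentence covers changes only.

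Protocol 10.1.2 (9) asks only for change from baseline in the iron measures and hepcidin. SAP section 9 does not list percent change among the departures from the protocol.

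**The concern.** Percent change is not symmetric. A marker can rise by any percentage but cannot fall by more than 100%, and two subjects whose values move by the same factor in opposite directions do not cancel. If one subject doubles and another halves, the mean percent change is (100 - 50)/2 = +25%, although there is no net change on the ratio scale. A t-test of zero mean percent change therefore does not test no change, and the confidence interval and MMRM estimate carry the same shift.

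Two features of this trial leave the shift uncorrected. There is no control arm, so no between-group difference can cancel it. Protocol 8.5.2 also has iron given to keep ferritin or TSAT above a threshold, so large individual ferritin rises are possible, and such values dominate an arithmetic mean of percent changes. At stake is how the percent-change p-values and intervals for iron handling are read.

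**Working it through.** **Inputs from the documents.** Twenty subjects in a single arm, set on feasibility with no power, effect size or SD (SAP 2.3); two-sided 5% tests (SAP 7.1.1); a t-test on untransformed percent change (SAP 7.5.2 (9)). The plan gives no figure for ferritin or hepcidin, so there is nothing to reproduce first.

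**Direction.** Let X0 and X1 be the positive baseline and follow-up values. If nothing changes, in the sense that X0 and X1 are exchangeable, then E[X1/X0] = E[(X1/X0 + X0/X1)/2]. Since r + 1/r is never below 2, this expectation is at least 1, so the expected mean percent change is zero or higher. No skewness assumption is needed.

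**Size (assumption).** Let X1/X0 be lognormal with geometric mean ratio G and log-scale SD s. Then

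mean percent change = 100 × (G × exp(s²/2) - 1).

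- No change (G = 1): exp(0.045) - 1 = +4.6% at s = 0.3; exp(0.125) - 1 = +13.3% at s = 0.5; exp(0.245) - 1 = +27.8% at s = 0.7.
- True 30% fall (G = 0.7): 0.7 × 1.0460 - 1 = -26.8%; 0.7 × 1.1331 - 1 = -20.7%; 0.7 × 1.2776 - 1 = -10.6%.
- True 20% fall (G = 0.8): -16.3%, -9.3% and +2.2%.

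**Test behaviour.** Simulation with n = 20, 40,000 runs per setting, two-sided 5%:

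| | s = 0.3 | s = 0.5 | s = 0.7 |
|---|---|---|---|
| No change: significant increase, percent change | 5.7% | 9.3% | 12.8% |
| No change: significant increase, log ratio | 2.5% | 2.5% | 2.5% |
| 30% fall: power, percent change | 99% | 58% | 21% |
| 30% fall: power, log ratio | >99% | 86% | 58% |
| 20% fall: power, percent change | 74% | 21% | 7% |
| 20% fall: power, log ratio | 88% | 47% | 27% |

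**When a fall disappears altogether.** The expected mean percent change reaches zero when s = sqrt(-2 ln G): 0.67 for a 20% fall, 0.85 for 30%, 1.01 for 40% and 1.18 for 50%.

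**MMRM.** A baseline covariate does not remove the shift. With complete data, the adjusted mean at the average baseline equals the raw mean. In simulation under no change at s = 0.5, with an assumed baseline log-SD of 0.8, it stayed at +13.4%.

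**What else the plan reports.** Under no change, the paired t-test on raw change rejects about 2% of the time in each direction. For a 30% fall at s = 0.5 and a per-visit log-SD of 0.8 (assumed), its power is about 67%, between percent change (58%) and log ratio (86%). Under the lognormal model, the population median percent change equals the geometric mean percent change. The sample median averages +0.4%, +1.0% and +1.9% under no change at s = 0.3, 0.5 and 0.7. For a true 30% fall it averages -29.3% at s = 0.5 and -28.6% at s = 0.7.

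**The case against.** The strongest reply is that percent change is only one of several planned readings. The same section tests raw change and models it by MMRM, and the time-course plots show change, or mean ferritin, rather than percent change. The median percent change will stand beside the mean. Neither raw change nor the median has a material upward bias. All of this stands. It means the iron analysis as a whole does not lose its ability to show a fall. It does not repair the p-value, interval and MMRM estimate that attach to mean percent change.

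The second reply is that the documents give no SD and never call ferritin or hepcidin right-skewed. That also stands. The direction of the bias does not need skew, but its size depends on variability. At s = 0.3 the problem is small: a 30% fall still reads -27% with 99% power.

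A reader might infer two stronger conclusions. One is that a real fall would be masked. The documents do not support this, because a 20% fall loses its sign only from s of about 0.67, and a 50% fall at s = 0.7 still reads -36% with 80% power. The other is that no change would generally be declared an increase. That holds for the expected mean, but a significant increase arises in only about 6% to 13% of trials for s from 0.3 to 0.7.

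The scope also has limits. For lipids the t-test is not specified on change rate, so only the MMRM part applies to triglycerides. EPO has no percent-change analysis. Finally, these are other endpoints with no stated success criterion, so the stakes are modest.

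**Conclusion.** The point holds in a limited form. A t-test of zero mean percent change has the wrong null, and the percent-change MMRM has the same bias. The direction follows from arithmetic alone. The size rests on assumed lognormal ratios, n = 20 and a log-SD of 0.3 to 0.7. Over that range, no change shifts upward by about 5 to 28 percentage points, the upward error rate is about 2 to 5 times the nominal 2.5%, and a true 30% fall is understated by about 3 to 19 points. The loss of power against the log scale is negligible at 0.3 and large at 0.5 and above. The point concerns the percent-change results for iron indices and hepcidin, and the percent-change MMRM for lipids. It does not extend to the raw-change results or the primary Hb analysis. It is a modest correction, worth making because it costs little.

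**What to change.** For ferritin and hepcidin, run the planned percent-change t-test and MMRM on log(value/baseline), and back-transform to a geometric mean percent change with 95% CI. Do the same for the lipid percent-change MMRM in SAP 7.5.2 (11), triglycerides in particular. Keep arithmetic and median percent change as descriptive summaries without p-values, and leave the raw-change analyses as they are. State in 7.5.2 (9) that percent change is modelled by MMRM, so that the text agrees with the table list, and record the added percent-change analysis in SAP section 9.

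The cost is a few lines of SAP wording and one transform in existing programs. SAP 6.5 does not allow zero as a substitute for values at or below the quantification limit, so the logarithm is defined. The downside is a slightly less familiar summary for an other endpoint. No analysis that the protocol asks for is lost.

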### 7.5.3 Adjustment for covariates

In the analysis of efficacy, in order to consider the effect of the measurement value of the first day of the treatment period on the change of each measurement, the analysis using the MMRM model (with compound symmetry [CS] for a variance-covariance matrix within subjects) should be conducted using the measurement value of the first day of the treatment period as a covariate in the general analysis including the analysis of the primary endpoint.

### 7.5.4 Handling of dropout or missing data

Provided in 6. Data handling.

### 7.5.5 Multicenter trial

For FAS, the following analysis should be conducted for each following endpoint for each site. Descriptive statistics of Hb values should be calculated at Week 24 of the treatment period (imputed by the LOCF method).

Descriptive statistics should be calculated for the mean dose of the study drug at Week 20 to Week 24 of the treatment period.

### 7.5.6 Subgroup analyses

The following analyses should be conducted for subpopulations based on the stratification factor for each endpoint in the table below in the FAS.

(1) Hb value at Week 24 of the treatment period

LSMean, standard error, and 2-sided 95% CI should be calculated using the MMRM model (with compound symmetry [CS] for a variance-covariance matrix within subjects).

(2) Study drug mean dose at Week 20 to Week 24 of the treatment period

Descriptive statistics should be calculated.

(3) Responder rates at Week 24 of the treatment period

With respect to the responder rate at Week 24 of the treatment period (proportion of subjects with increased Hb value by  $\geq 1.0$  g/dL from the first day of the treatment period), the number of responders, proportion, and 95% CI (Clopper-Pearson [Exact] method) of the proportion should be provided.

(4) Target Hb achievement rate at Week 24 of the treatment period

The number, proportion, and 95% CI (Clopper-Pearson [Exact]) method) of the proportion of subjects with Hb levels within the target range (10.0 g/dL to  $<12.0$  g/dL) should be provided.

Table 7.5.4 Subgroup analysis of efficacy

Endpoints	Stratification factor	Stratified category
1. Hb value at Week 24 of the treatment period 2. Study drug mean dose at Week 20 to Week 24 of the treatment period 3. Responder rates at Week 24 of the treatment period 4. Target Hb achievement rate at Week 24 of the treatment period	Sex	Male, Female
	Age at time of consent (years)	<65, ≥65 <75, ≥75
	Dry weight (kg) on the first day of the treatment period	<60, ≥60
	BMI (kg/m  ) on the first day of the treatment period	<25, ≥25
	Underlying cause of CKD	Diabetes, hypertension, autoimmune/glomerulonephritis/vasculitis, interstitial nephritis/pyelonephritis, cystic/hereditary/congenital disease, neoplasm/tumor
	Duration of nephrogenic anemia (years)	<1, 1 to <5, ≥5
	Complication	Presence or absence of hypertension, diabetes, dyslipidemia
	Hb value (g/dL) on the first day of the treatment period	<9, 9 to <10, ≥10
	Liver function test (U/L) on the first day of the treatment period	AST and ALT both not more than the upper limit of normal, either above the upper limit of normal and both ≤ 2 times the upper limit of normal, either > 2 times the upper limit of normal
	CRP (mg/dL) on the first day of the treatment period	<0.31, ≥0.31
	Serum ferritin (ng/dL) on the first day of the treatment period	Divide the number of subjects into three categories based on the tertile
	TSAT (%) on the first day of the treatment period	Divide the number of subjects into three categories based on the tertile
	Smoking status	3 Categories: Never smoked, ex-smoker, current smoker
	Administration of oral iron on the first day of the treatment period	Yes or No
	Treatment with oral iron supplement at Week 24 of the treatment period	Yes or No
	Iron-containing phosphate binders on the first day of the treatment period	Yes or No
	Iron-containing phosphate binders at Week 24 of the treatment period	Yes or No
Wash-out of prior treatment ESAs	Yes or No	
CYP2B6 inducer combination *	Yes or No	

\* List of CYP2B6 inducers obtained from The Metabolism and Transport Drug Interaction Database (DIDB®).

### **7.5.7 Multiple comparison and multiplicity**

In this study, no multiplicity problem occurs.

## **7.6 Safety analysis**

The safety analysis population should be analyzed. When necessary, frequency and proportion should be calculated for discrete variables and descriptive statistics for continuous variables.

### **7.6.1 Adverse events and adverse drug reactions**

#### **7.6.1.1 Summary of adverse events and adverse drug reactions**

The number (number of subjects with adverse events) and proportion of subjects in whom the following adverse events are observed at least once after the administration of the study drug to the end of the follow-up period should be calculated.

- Adverse event
- Adverse drug reaction
- Serious adverse event
- Serious adverse drug reaction
- Adverse event leading to discontinuation
- Adverse events leading to dose reduction or interruption of study drug
- Adverse event leading to death (adverse event of fatal outcome)

#### **7.6.1.2 Individual adverse events**

For adverse events, adverse drug reactions, serious adverse events, non-serious adverse events, serious adverse drug reactions, adverse events leading to discontinuation of study drug, adverse events leading to dose reduction or interruption of study drug, and adverse events leading to death, the number of subjects and incidence rate should be calculated for each adverse event classified by SOC and PT in MedDRA/J 2x.x (hereinafter the same). The SOC is shown in the order of international consensus, and the PT is shown in descending order of the number of subjects with events (if the number is the same, ascending order of PT Code).

#### **7.6.1.3 Adverse events by severity**

The number of subjects and incidence rate should be calculated for adverse events and adverse drug reactions by severity for the overall and for individual events classified by SOC and PT.

The tabulation method by severity (severe, moderate, mild) is as follows.

- (1) When adverse events of different severity occur in the same subject, the most severe adverse event should be counted as one subject.

- (2) When multiple adverse events of the same severity occur in the same subject, the same severity should be counted as 1 subject.
- (3) When the same subject experienced the same adverse event multiple times, the most severe adverse event should be counted as 1 subject.

#### **7.6.1.4 Adverse event by time of onset**

The number and incidence rate of subjects with adverse events and adverse drug reactions should be calculated for adverse event and adverse drug reaction by time of onset (every 12 weeks) for the overall and for individual events classified by SOC and PT. For the calculation of the incidence rate, the number of subjects at each evaluation time point is used as the denominator. (Tabulation unit: From the first day of the treatment period [Day 1] to Day 84, after Day 85)

